9.7 Vital Signs and Physical Evaluations

Vital sign measurements include oral temperature, sitting pulse, sitting systolic blood pressure, and sitting diastolic blood pressure. Vital signs will be collected at the screening visit (Visit 00A), prior to administration of study product (Visit 01A), at Visit 01H (12 hours \pm 10 minutes post-dose), at Visit 01J (24 hours \pm 1 hour post-dose), at Visit 01L (48 hours \pm 1 hour post-dose), at Visit 01M (72 hours \pm 4 hours post-dose), at Visit 01N (96 hours \pm 4 hours post-dose), Visit 02 (12 days \pm 2 days post-dose) and any ET. Vital signs will be tabulated by visit and renal impairment group and listed ([Table 72](#) through [Table 76](#) and [Listing 13](#)).

A PE will be performed at the screening visit (Visit 00A). A targeted PE may be performed at all in person study visits and any ET visit if indicated based on interim medical history. The following body systems will be assessed at the screening visit and then as indicated for subsequent targeted PEs: skin, head, eyes, ears, nose and throat, thyroid, neurological system, chest and lungs, cardiovascular system, abdomen, lymph nodes, musculoskeletal system, and extremities ([Listing 14](#)). A summary of abnormal physical exam findings will be shown in [Table 77](#). Height and weight will only be collected during screening and will be summarized in the demographics tables ([Table 12](#) and [Table 14](#)).

9.8 Concomitant Medications

Concomitant medications will be coded to the Anatomical Therapeutic Classification using the WHO Drug Dictionary. The use of prior and concomitant medications taken during the study will be recorded on the eCRFs. A by-participant listing of concomitant medication use will be presented ([Listing 16](#)). The use of concomitant medications during the study will be summarized by ATC1 code, ATC2 code, and renal impairment group for the Safety population ([Table 78](#)).

9.9 Other Safety Measures

An ECG will be performed at the Screening Visit 00A and Visit 01N. If the result is abnormal, it may be repeated per the investigators discretion. The ECG intervals (QTcF), including change from baseline, will be summarized at the Screening Visit 00A and Visit 01N (96 hours \pm 4 hours post-dose), including any repeated ECG measurements, using descriptive statistics ([Table 79](#)).

Individual ECG interval measurements will be provided in [Listing 15](#).

10 PHARMACOKINETICS

PK analyses will be performed using NCA. PK concentrations and noncompartmental parameters will be summarized by renal impairment group. Statistics include the arithmetic mean, median, SD, GM, CV, min, and max. PK parameters of exposure (AUC_{last}, AUC_∞, and C_{max}) will be compared between impairment groups using ANOVA models with or without random effects. T_{max} will be compared using 90% confidence intervals calculated using the inverted rank score method. Concentrations below the quantitation limit (BQL) prior to first measurable concentration will be imputed as zero. The first BQL concentration reported in the plasma concentrations after the last measurable concentration may be imputed for the purpose of parameter estimation as the LLOQ divided by 2 only if 1) needed to estimate λ_z, 2) all other λ_z estimation criteria are met, and 3) if a visual predictive check of the imputed value appears to be consistent with the observed elimination trend. All other BQL samples will be treated as missing. Imputed concentration values will only be used for plasma parameter estimation by NCA and not included in concentration summaries, however, imputed BQL values will be indicated by imputation method in listings with methods clarified in the footnote and denoted in figures.

10.1 Summary of Pharmacokinetic Sampling and Sample Properties

The plasma PK of a single dose of pretomanid will be assessed from serial blood samples collected up to 1 hour pre-dose (Day 1) and at multiple time points post dosing: 1, 2, 4, 5, 6, 8, 12, 16, 24, 36, 48, 72, and 96 hours.

The urine PK of a single dose of pretomanid will be assessed from urine collected up to 1 hour pre-dose, 0-4, 4-8, 8-12, 12-24, 24-48, 48-72, and 72-96 hours post-dose.

Samples with bioanalytical errors or quality issues reported by the laboratory will be excluded. Collection times of samples missing the actual collection time will be imputed using the nominal collection time. Such samples will be identified in the analysis report ([Listing 22](#)).

10.2 Pharmacokinetic Analysis

10.2.1 Concentration Summaries

Drug plasma concentrations will be listed by renal impairment group, and participant. Out of sample time window and PK analyses-excluded samples will be indicated, as will BQL values that were imputed for the purposes of parameter estimation ([Listing 22](#)). The listings will also indicate the nominal and actual time associated with the sample (nominal time is defined as the planned time in hours since the first dose).

Potentially important bioanalytical errors and their effect on the PK analysis will be discussed.

Plasma drug concentrations will also be summarized by impairment group ([Table 80](#) through [Table 83](#)) and plotted.

[Figure 22](#) through [Figure 25](#) (linear) and [Figure 29](#) through [Figure 32](#) (semilogarithmic) will plot all participant plasma PK profiles together by renal impairment group, as linear and semilogarithmic plots.

Linear plots of participants with renal impairment with their matched controls ([Figure 26](#), [Figure 27](#), and [Figure 28](#)).

Linear plots of plasma mean concentration curves will be shown in [Figure 33](#), with error bars representing ± 1 SD.

Semi-logarithmic plots of geometric mean plasma concentration curves will be shown in [Figure 34](#).

10.2.2 Pharmacokinetic Parameters

10.2.2.1 Plasma Pharmacokinetic Parameters

NCA PK parameters will be calculated using the actual post-dose time. Samples with concentrations greater than the LLOQ will be considered for the estimation of λ_z . Imputing the first BQL concentration following the last concentration greater than LLOQ to LLOQ divided by 2 will be considered on a participant-by-participant basis for participants where the λ_z acceptance criteria are not met by the observed data greater than the LLOQ. λ_z will be computed from the log-transformed concentration data. The correlation between time and concentration at the time points used to estimate λ_z should be sufficiently high (adjusted- $R^2 > 0.9$) for λ_z . Additionally a minimum of three concentrations in the terminal elimination phase will be used for the calculation of λ_z . All concentrations used to calculate λ_z must come from samples taken at or after T_{max} . The concentrations used to calculate λ_z along with the number of concentrations used for the calculation will be included in the participant listing ([Listing 22](#)).

The plasma AUC will be computed using the linear-up log-down (linear-log) trapezoidal method in Phoenix WinNonlin (Certara, Radnor, PA).

All plasma PK parameters will also be summarized by renal impairment group using descriptive statistics ([Table 84](#) through [Table 87](#)). Additionally, participant-level PK parameters will be presented in the tables in the final report.

The following parameters will be estimated: C_{max} , T_{max} , AUC_{last} , AUC_{∞} , % AUC_{ex} , $t_{1/2}$, λ_z , CL/F , and V_d/F .

See Section 3.3.1 for parameter definitions.

10.2.2.2 Urine Pharmacokinetic Parameters

NCA PK parameters will be calculated using the actual post-dose collection window times. Samples with concentrations greater than the LLOQ will be considered for the estimation of urine PK parameters. Phoenix WinNonlin urine NCA models 210-212 will be used to estimate all urine PK parameters. Urine concentrations and both nominal and actual collection windows will be listed in [Listing 23](#).

All urine PK parameters will also be summarized by renal impairment group using descriptive statistics ([Table 88](#) through [Table 91](#)). Additionally, participant-level urine PK parameters will be presented in the tables in the final report.

The following parameters will be estimated ([Listing 24](#)): $Ae_{(0-t)}$, $Ae\%Dose$, and CL_R .

See Section 3.3.1 for parameter definitions.

10.2.3 Comparison of Impairment Groups

If at least one matching participant in the healthy volunteer group is available in the renal impairment groups, the following random effects ANOVA model will be used to test for a group by site interaction and if significant ($p < 0.10$), estimate group and site level parameters and compare impairment groups for primary PK parameters:

$$Y_{ij} = \mu + \tau_{[ij]} + \alpha_i + \gamma_k + \tau_{[ij]}\gamma_k + \varepsilon_{ij}$$

Here, i represents the matched block, j represents the participant in matched block i , Y_{ij} is the log-transformed PK parameter for participant j in block i , $\tau_{[ij]}$ is the impairment group effect for the group in which

participant j in block i belongs, α_i is the random group effect for matched block i , γ_k is the indicator variable for the fixed effect of study site k , and $\tau_{[ij]}\gamma_k$ is the interaction between participant impairment group and site. If no matching participants are available with PK parameters, the standard fixed effects ANOVA model without random effect α_i will be used. The following SAS code may be used to estimate the model above:

```
proc mixed data=impairment;
  class match group (ref="Matched Control") site;
  model logPKpar = group site group*site / solution cl alpha=0.10;
  random match;
  lsmeans group site group*site;
  run;
```

The estimates from this model can be exponentiated to get fold differences.

If the group by site interaction is not significant then the following model will be used to estimate group level parameters:

$$Y_{ij} = \mu + \tau_{[ij]} + \alpha_i + \gamma_k + \varepsilon_{ij}$$

The following SAS code may be used to estimate the model above:

```
proc mixed data=impairment;
  class match group (ref="Matched Control") site;
  model logPKpar = group site / solution cl alpha=0.10;
  random match;
  lsmeans group;
  run;
```

The estimates from this model can be exponentiated to get fold differences.

Pairwise fold differences in drug exposure will be calculated to compare each of the mild, moderate, and severe renal impairment groups with healthy controls. Fold difference and mean will be estimated by ANOVA and shown using 90% confidence intervals. An adjustment to the confidence level for multiple comparisons is not planned ([Table 92](#)).

T_{\max} will be summarized in each impairment group using the median, and group differences will be assessed using nonparametric confidence intervals computed using the inverted rank score method ([Table 93](#)). Medians and confidence intervals will also be computed for each site. If the confidence intervals do not overlap between sites, then the T_{\max} will also be summarized by site.

Summary box plots of PK parameters by impairment group (and site if appropriate) will also be presented ([Figure 35](#), [Figure 36](#), [Figure 37](#), [Figure 38](#), [Figure 39](#), and [Figure 40](#)).

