6 GENERAL STATISTICAL CONSIDERATIONS

6.1 General Principles

There are several units of analysis in this study. For the PK analysis, the unit of analysis will be the reported pretomanid concentrations, however, PK profiles in both plasma and urine will be evaluated at the participant level. Medical history, concomitant medications, AEs, SAEs, clinical laboratory, physical examination (PE), vital signs, and ECG will be presented at the participant level, and summaries will be presented at the study and renal impairment group level.

All continuous variables will be summarized using the following descriptive statistics: n (non-missing sample size), arithmetic mean, standard deviation (SD), median, minimum (min), and maximum (max). PK concentration and parameter summaries will additionally report the geometric mean (GM) and coefficient of variation (CV). Minima and maxima will be reported to the same precision as the raw values, means and medians will be presented to one extra decimal place than the raw values and standard deviations will be reported to 2 extra decimal places than the raw values.

The frequency and percentages (based on the non-missing sample size) of observed levels will be reported for all categorical measures. Percentages will be rounded to one decimal place (i.e. XX.X%) except for 100% which will be reported with no decimal places. In general, all data will be listed, sorted by impairment group and participant, and when appropriate by visit number and parameter within participant. In general, the last recorded value prior to study drug administration will be considered as baseline. Changes from baseline will be calculated as the follow-up visit value minus the corresponding baseline value. All summary tables will be structured with a column or row block for each impairment group in the order (Mild Renal Impairment, Moderate Renal Impairment, Severe Renal Impairment, Matched Controls) and will be annotated with the total population size relevant to that table/impairment group, including any missing observations. More details will be provided for reporting pharmacokinetic results in Section 10.

Estimates and CIs will be utilized rather than formal hypothesis tests.

No formal hypothesis tests are planned for safety analyses, but safety data will be collected and analyzed.

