6.7 Multicenter Studies

This study is planned to be conducted at multiple sites; however, data will be pooled across all clinical sites for analysis with the exception of demographics summaries and PK summaries that may be presented both overall and by site.

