6.8 Multiple Comparisons/Multiplicity

While multiple PK parameters will be estimated in two sources, plasma and urine, no hypothesis testing will be performed. Summary statistics and confidence intervals will be used rather than formal hypothesis testing.

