17 LISTING OF TABLES, FIGURES, AND LISTINGS

Table, figure, and listing shells are presented in Appendices 1, 2, and 3.

[Global Programming Note: Only columns, legends, and any other impairment group indicators in the table, figure, and listing shells that were enrolled in the study will be included in the outputs. For example, if only the Severe Renal Impairment and Matched control groups are enrolled, columns, figure legends, or other indicators for the Mil and Moderate Renal Impairment groups may be removed.

The Severe Renal Impairment arm will be displayed in two separate columns as "Severe Renal Impairment" and "ESRD, Not on Dialysis" in tables and figures.]

APPENDICES

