14.6 Pharmacokinetics Results

Table 81: Individual and Summary Statistics for Plasma Concentrations by Nominal Time (hours) – Mild Renal Impairment Group

	Pre-Dose	1	2	4	5	6	8	12	16	24	36	48	72	96
001														
002														
003														
N														
N Not Evaluable														
Number < LLOQ^a														
Mean														
SD														
Min														
Median														
Max														
Notes: ^a LLOQ = 10 ng/mL														

Tables with similar format to Table 77:

Table 82: Individual and Summary Statistics for Plasma Concentrations by Nominal Time (hours) – Moderate Renal Impairment Group

Table 83: Individual and Summary Statistics for Plasma Concentrations by Nominal Time (hours) – Severe Renal Impairment Group

Table 84: Individual and Summary Statistics for Plasma Concentrations by Nominal Time (hours) – Matched Controls

Table 85: Individual and Summary Statistics for Noncompartmental Plasma PK Parameters – Mild Renal Impairment

Participant ID	C _{max} (µg/mL)	T _{max} (hr)	AUC _{last} (µg*h/mL)	AUC _∞ (µg*h/mL)	%AUC _{ex} (µg*h/mL)	t _{1/2} (hr)	λ _z	CL/F (L)	V _d /F (L)
001									
002									
003									
N									
Mean									
SD									
Min									
Max									
CV %									
GM									

*Tables with similar format to Table 85:***Table 86: Individual and Summary Statistics for Noncompartmental Plasma PK Parameters – Moderate Renal Impairment****Table 87: Individual and Summary Statistics for Noncompartmental Plasma PK Parameters – Severe Renal Impairment****Table 88: Individual and Summary Statistics for Noncompartmental Plasma PK Parameters – Matched Controls**

Table 89: Individual and Summary Statistics for Noncompartmental Urine PK Parameters – Mild Renal Impairment

Participant ID	Ae _(0-t) µg	Ae%Dose	CL _R (L/h)
001			
002			
003			
N			
Mean			
SD			
Min			
Max			
CV %			
GM			

Tables with similar format to Table 89:

Table 90: Individual and Summary Statistics for Noncompartmental Urine PK Parameters – Moderate Renal Impairment**Table 91: Individual and Summary Statistics for Noncompartmental Urine PK Parameters – Severe Renal Impairment****Table 92: Individual and Summary Statistics for Noncompartmental Urine PK Parameters – Matched Controls**

Table 93: Estimated Impairment Group Fold Change for Noncompartmental PK Parameters

[Implementation Note: The site column will only be included if the group by site interaction is significant at a p-value < 0.10 level.]

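### A p < 0.10 group-by-site test chooses the model for the AUC and Cmax fold changes, which narrows the 90% intervals too far and leaves the estimated ratio undefined

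*SAP*

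**What the plan says.** SAP 10.2.3 gives a random-effects ANOVA for each log-transformed exposure parameter, with group, site, their interaction and a random matched block. This model "will be used to test for a group by site interaction and if significant" (p < 0.10) it also estimates group and site parameters and compares the groups. If the test is not significant, a model without the interaction is used. The section adds that "Fold difference and mean will be estimated by ANOVA and shown using 90% confidence intervals", and says of each model that "The estimates from this model can be exponentiated to get fold differences".

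The fold-change shell (Table 93 in SAP Appendix 1) repeats the gate: "The site column will only be included if the group by site interaction is significant at a p-value < 0.10 level". The shell has an All Sites block, one block per site, and columns for AUClast, AUC∞ and Cmax.

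Three other sections bear on this:
- SAP 6.1: "Estimates and CIs will be utilized rather than formal hypothesis tests".
- SAP 6.8: "no hypothesis testing will be performed. Summary statistics and confidence intervals will be used rather than formal hypothesis testing".
- SAP 6.7 pools data over sites but allows "PK summaries that may be presented both overall and by site", with no test attached.

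SAP 17 foresees outputs "if only the Severe Renal Impairment and Matched control groups are enrolled", that is, a final dataset of 12 participants.

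**The concern.** The sections disagree on whether any test is used. Beyond that wording conflict, the gate has three consequences.

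1. The test and the interval share one error estimate. The gate fires more often when that estimate is low by chance, and the interval that follows is then too narrow.
2. The branches weight sites differently. Default LSMEANS in the interaction model weights the two sites equally, while the additive group effect weights them by enrolment. At an uneven split these are different ratios if the sites differ, and the SAP does not name the one it wants.
3. Table 93 has one Site column for three parameters, and nothing says which parameter's test controls it.

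A smaller point concerns the illustrative code. In the interaction branch the SOLUTION group coefficient is the ratio at the reference (last) site only, so exponentiating it does not give an overall fold difference. That code prints no 90% interval for the All Sites ratio, and neither branch prints an interval for the group means.

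At stake are the final fold changes and 90% intervals. The Part A decision is outside this point, because Protocol 10.1 refers its details to the PK Manual.

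**Working it through.** **Inputs from the documents.** CV 20%, true ratio 2, six per group, no within-pair correlation (SAP 5); two sites (Protocol Summary); gate at p < 0.10 and 90% intervals (SAP 10.2.3).

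**Assumptions.** The six pairs split 3/3, 4/2 or 5/1 between sites, both members of a pair attend the same site, and degrees of freedom follow the PROC MIXED default (containment).

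**Check on the inputs.** Log SD = √ln(1 + 0.2²) = 0.198. SE of the log ratio = 0.198 × √(2/6) = 0.114. A noncentral t with 5 df gives a 69.7% probability that the lower 90% bound is at least 1.5, which matches the roughly 70% in SAP 5. The SAP gives no coverage figure for the two-step rule.

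**Formulas, paired analysis.** Let d̄1 and d̄2 be the mean within-pair log ratios at sites with n1 and n2 pairs, and s the SD of those log ratios.
- Gate: |d̄1 − d̄2| / (s√(1/n1 + 1/n2)) against t with 4 df.
- Interaction branch: (d̄1 + d̄2)/2 ± t(4) × s × ½√(1/n1 + 1/n2).
- Additive branch: mean of all six ± t(5) × s/√6, with s re-estimated on 5 df.

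The gate and the interaction interval use the same s. Given firing, the mean error-variance estimate is 0.40 of its true value. In addition, the correlation between d̄1 − d̄2 and the site average is (n2 − n1)/(n1 + n2) = 0, −0.33 and −0.67 for the three splits. At uneven splits, firing therefore also selects datasets whose site average is far off, which is why coverage worsens from 3/3 to 5/1.

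**No true site difference, 12 participants, paired (1,000,000 replicates).**

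| | 3/3 | 4/2 | 5/1 |
|---|---|---|---|
| Gate fires | 10.0% | 10.0% | 10.0% |
| All Sites coverage given firing | 74.4% | 69.8% | 54.1% |
| Additive model, same datasets | 89.9% | 90.2% | 89.8% |
| Two-step rule overall | 88.4% | 88.0% | 86.4% |

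The last row follows from the others: 0.900 − 0.10 × (0.899 − 0.744) = 0.884; 0.900 − 0.10 × (0.902 − 0.698) = 0.880; 0.900 − 0.10 × (0.898 − 0.541) = 0.864.

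**Other analysis versions (3/3, 4/2, 5/1).**
- Unpaired least squares: given firing 82.1%, 76.8%, 58.7%; overall 89.2%, 88.7%, 86.8%, against 90.0% for the additive model.
- REML with random match as coded, pair correlation 0 to 0.5: overall 87.1–88.3%, 86.5–87.7%, 84.8–86.1%, against 88.6–89.8% for the ungated additive model.
- A second simulation, with correlations 0 to 0.6, some blocks spanning sites and the fixed-effects fallback: loss 0.7–3.8 points. The single-site rows, shown only when the gate fires, covered 29–73%.
- 36 participants: overall 89.3–89.8%, 88.9–89.3%, 88.0–88.4%.

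**True 1.5-fold site difference (assumed), larger ratio at the larger site, 12 participants, paired.** Site ratios are 2√1.5 = 2.45 and 2/√1.5 = 1.63. The equally weighted target is 2.00. The enrolment-weighted target is 2 × exp[((n1 − n2)/6) × ln(1.5)/2].

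| | 3/3 | 4/2 | 5/1 |
|---|---|---|---|
| Enrolment-weighted target | 2.00 | 2.14 | 2.29 |
| Gate fires | 43% | 40% | 30% |
| Two-step, equal-weight target | 90.0% | 88.0% | 79.1% |
| Two-step, enrolment-weighted target | 90.0% | 86.4% | 80.3% |
| Additive, its own target | 95.6% | 95.1% | 93.6% |
| Ungated site-averaged contrast, its own target | 90.0% | 90.0% | 90.0% |

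**SOLUTION coefficient.** After a false-positive interaction at 3/3, the reference-site ratio is off by a median of 1.22-fold (paired) to 1.24-fold (unpaired), against 1.08-fold for the all-sites ratio.

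**The case against.** The strongest reply is that conditional coverage is the wrong yardstick. In the datasets where the gate fires, an ungated interaction contrast gives the same interval and the same poor coverage, yet it covers 90% overall. That is correct, and the overall loss is the fair summary. But the gate is what replaces the additive interval in exactly those datasets, where the additive interval would still cover about 90%.

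Other points have some force:
- The overall loss is small at 3/3 and with 36 participants, and larger losses need an uneven split that the documents do not report. This stands.
- The change of target needs a true site difference. Every participant gets the same supervised dose with a specified meal, and a 1.5-fold difference has no source in the documents. This also stands; the figures show what follows if sites differ.
- The SAP does not state outright which model fills the All Sites rows. It is inferred from 10.2.3, which says the model retained by the test compares the groups. If the inference is wrong, the source of those rows is unspecified and still needs stating.
- SAP 6.8 is the multiplicity section and may not have had a model check in mind. Its wording carries no such limit.
- The code is only illustrative, and the prose already requires 90% intervals. That is why the code point is minor.

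**Conclusion.** The concern holds. SAP 10.2.3 conflicts with 6.1 and, most plainly, with 6.8. The two-step rule gives intervals below their nominal level.

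With 12 participants and no true site difference, the gate's own cost in coverage (additive minus two-step, across the paired, unpaired and REML versions) is 0.8–1.6 points at 3/3, 1.3–2.1 at 4/2 and 3.2–3.9 at 5/1. That average is modest, but it is concentrated in the roughly one analysis in ten per parameter where the gate fires. If sites truly differ and the split is very uneven, the rule holds its level for neither possible target.

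The mechanism and the wording conflict do not depend on the assumptions. The sizes depend on the 20% CV, the assumed site split, how pairs fall across sites, the within-pair correlation and the df method.

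**What to change.** Remove the significance gate and prespecify one model for all three parameters and for the All Sites rows of Table 93.

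- Primary: group, site and random match, with `lsmeans group / diff cl alpha=0.10`. State that it targets the ratio averaged over enrolled participants.
- Site results: geometric means and ratios by site, shown descriptively, as SAP 6.7 already allows.
- Sensitivity: the site-averaged contrast from the interaction model with its 90% interval, reported regardless of any p-value and not read from the SOLUTION coefficient.
- Make SAP 6.1, 6.8, 10.2.3 and the Table 93 note agree.

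The cost is wording, one table note and a few SAS options. There are statistical downsides. If the sites truly differ by 1.5-fold, the additive interval is conservative at 3/3 (95.6%, paired). At 5/1 it covers the equally weighted ratio only 73–80% of the time across the analysis versions, much like the current rule (77–79%). The sensitivity contrast covers that case but is wider: median half-width 1.25-, 1.27- and 1.35-fold at 3/3, 4/2 and 5/1, against 1.24-fold for the additive model with no site difference.
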